8.0 Intervention Description

All subjects will have the standard physical therapy visits conducted by the PTs at the Colonel Glenn facility. Participants will undergo standard physical therapy sessions at UAMS' Colonel Glenn facility either with or without the use of the BFR apparatus. Subjects will progress through the goals set by their therapist as their condition permits. Physical Therapists will be the same (Colonel Glenn therapists) for both intervention and standard of care groups to standardize treatment. The physical therapists participating in the study have all demonstrated proficiency in the BFR approach. Briefly, the BFR apparatus consists of an electronically controlled pneumatic tourniquet(s) that is placed (in this study) on the upper thigh(s) and inflated during exercise. The control mechanism continuously adjusts the air pressure to maintain the operator-chosen percentage of arterial occlusion (e.g. 75%) as determined by the blood pressure of that limb for a determined amount of time (e.g. for the duration of 4 sets of 30:15:15:15 ~~3 sets of 8~~ repetitions of knee flexion/extension). The tourniquet is deflated at specific intervals. The BFR apparatus is used primarily in the early stages of rehabilitation with the goal of increasing the strength and endurance of that limb at a faster rate than performing the exercises without BFR.

9.0 Outcome Measures

9.1 10-meter Walking Speed

This test is performed in a quiet, well-lit hallway. Subjects are instructed to walk as quickly as they can without running through a 20-meter course. The middle 10 meter distance is timed using stationary timer devices. Subjects will be accompanied by study staff for safety purposes but will not help the subject unless required.

Use of Blood Flow Restriction + Standard of Care Physical Therapy to Improve Functional Outcomes after
Anterior Cruciate Ligament Reconstruction
PI: [name].
Institution: UAMS
Sponsor: UAMS

9.2 Maximum Voluntary Contraction

Using the Cybex Dynamometer, isometric testing will be used to measure maximal muscle strength defined as the highest peak torque (Nm) obtained during knee extension of each leg separately. Subjects will be securely seated in the machine to ensure safety and stability for the test. Adjustments will be made to align the knee and ankle with the testing equipment. After a practice set to familiarize participants with the equipment, subjects will have three attempts of 5 seconds each separated by two minutes of rest between attempts. The highest peak torque reading will be recorded. Subjects will be measured first on the surgical right leg and next on the non-surgical left leg. If a subject has recently (~1 week) performed this same measurement as part of their prescribed physical therapy, study staff will ask for the results. If results are provided, duplicate testing will not be performed.

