5.0 Study Visits

Use of Blood Flow Restriction + Standard of Care Physical Therapy to Improve Functional Outcomes after
Anterior Cruciate Ligament Reconstruction
PI: [name].
Institution: UAMS
Sponsor: UAMS

Subjects will be required to wear a mask. If they do not have one, a mask will be provided to them by the study staff.

Visit 1: This visit will take place at the UAMS RIOA prior to surgery. At this visit, informed consent discussion will be held. Study staff will use appropriate PPE. This visit is expected to take less than about one hour. If a subject consents, their vital signs will be measured (blood pressure, oxygen saturation) while at rest for at least 10 minutes for exclusion criteria. Randomization will occur. [name] will be notified via email as to which group each enrolled subject has been randomized. He will then communicate this to the relevant physical therapists at the Col. Glenn facility.

Visit 2: This fasted visit will occur approximately 7-10 days before surgery. Subjects will be asked to fast for 8 hours, avoid caffeine and alcohol for 12 hours, and avoid strenuous exercise for 24 hours prior to this visit. Subjects will undergo body composition testing (DEXA, InBody). After a 5 minute warm up (stretching/walking/cycling as tolerated), strength testing of each leg, and 10-meter walking speed test will commence. This visit is expected to take about 1 hour.

Visit 3: This visit will take place at the UAMS RIOA approximately 8 weeks after surgery. Subjects will be asked to fast for 8 hours, avoid caffeine and alcohol for 12 hours, and avoid strenuous exercise for 24 hours prior to this visit. At this visit, a 5-minute warm up, physical, functional, and body composition testing (DEXA, InBody) will take place (see Study Calendar). Future study visits will be scheduled. This visit is expected to take about 1 hour.

Visit 4: This visit will take place at the UAMS RIOA approximately 12 weeks after surgery. Subjects will be asked to fast for 8 hours, avoid caffeine and alcohol for 12 hours, and avoid strenuous exercise for 24 hours prior to this visit. At this visit, a 5-minute warm up, physical, functional, and body composition testing (DEXA, InBody) will

Use of Blood Flow Restriction + Standard of Care Physical Therapy to Improve Functional Outcomes after
Anterior Cruciate Ligament Reconstruction
PI: [name].
Institution: UAMS
Sponsor: UAMS

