take place (see Study Calendar). Future study visits will be scheduled. This visit is expected to take about 1 hour.

Visit 5: This visit will take place at the UAMS RIOA approximately 16 weeks after surgery. Subjects will be asked to fast for 8 hours, avoid caffeine and alcohol for 12 hours, and avoid strenuous exercise for 24 hours prior to this visit. At this visit, a 5-minute warm up, physical, functional, and body composition testing (DEXA, InBody) will take place (see Study Calendar). Future study visits will be scheduled. This visit is expected to take about 1 hour.

As part of PT, subject's level of pain will be ascertained using a 0-10 point scale at the onset of their PT visits. They will also be asked to complete the Fear-Avoidance Beliefs Questionnaire at some visits. The ROM of their surgical knee will be measured at certain times. In addition, progression towards UAMS' 'Return to Sport' measurements are performed and documented. Some of these data elements will be retrieved from the therapist's notes in Epic by study staff.

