6.0 Blinding

The study is a single-blind, randomized, controlled trial (RCT). While participants cannot be blinded since BFR is the intervention being evaluated, key investigators and outcomes assessors will be blinded to treatment assignment, making this a single-blind RCT from the investigators' perspective.

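### Section 9.2 lets a therapy MVC replace the study MVC, so strength values probably obtained with knowledge of the arm could enter a comparison that section 6.0 describes as assessor-blinded

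*Combined protocol and SAP*

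**What the plan says.** - **Section 9.2** covers a subject who has, within about a week, "performed this same measurement as part of their prescribed physical therapy". Study staff ask for the result, and "If results are provided, duplicate testing will not be performed". The therapy value then stands in for the study value.
- **Section 6.0** states that "key investigators and outcomes assessors will be blinded to treatment assignment". It carves out nothing for MVC. Section 2.1 likewise promises a blinded tester for the functional outcomes.
- **Section 8.0** says who runs prescribed therapy: "All subjects will have the standard physical therapy visits conducted by the PTs at the Colonel Glenn facility". Sessions take place with or without the cuff.
- **Section 5.0**, after describing how group assignment is notified, says: "He will then communicate this to the relevant physical therapists at the Col. Glenn facility". The therapists therefore know the arm.
- **Section 5.0** also asks subjects to "avoid strenuous exercise for 24 hours prior to this visit", and **section 9.8** fixes the order of tests at each visit.
- **Section 10.1** compares the groups on each strength and functional outcome at the mid-point and final visits. It uses ANCOVA on the pretest value, two-sided at 0.05, with no term or sensitivity analysis for where a value came from.

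**The concern.** Strength is part of the specific aim in section 3.0, and MVC is the only dynamometer measure of it. A maximal contraction depends on how hard the subject tries and how strongly the tester urges. Section 6.0 accepts that subjects know their arm, so blinding the tester is the only blinding available for this outcome. The substitution rule gives that up for any value brought in from therapy.

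A substituted value can also differ in other ways. It may be about a week old, and nothing applies the 24-hour exercise restriction or the fixed test order to a therapy session. The protocol does not require the source, date or tester of an MVC to be recorded, so a reader of the results could not tell how many values were affected.

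The pilot is meant to supply data for powering later studies and to confirm methods (sections 10.1 and 2.1), so a weakness in the strength data would carry into that planning.

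**Working it through.** **Does the text conflict?** Section 9.2 admits a value from prescribed therapy. Section 8.0 places that therapy with the Colonel Glenn therapists, and section 5.0 tells them the allocation. Section 6.0 says outcome assessors do not know it. No section requires a blinded person to take a therapy MVC. The conflict is real whenever the rule is used. Because no section names who would run such a test, the right word is that the tester *probably* knows the arm.

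**When could it apply?** The Study Schema starts prescribed therapy with or without BFR after surgery. Exposure is therefore mainly at Visits 3 to 5, and the pre-surgery covariate is probably unaffected. Section 5.0 says of the therapy clinic's Return to Sport assessments that "measurements are performed and documented", but it does not say that they include MVC.

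**Timing.** Postoperative visits are at 8, 12 and 16 weeks (section 1.0), so the gap is 4 weeks. A value one week old is 1/4 = 25% of that gap.

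**Size.** The plan states no SD, effect size, correlation or power, so there is no figure to reproduce. The inputs for illustration are:
- from the documents: 20 completers (section 4.0) allocated 1:1 (section 7.0), taken as n = 10 per arm; two-sided 5% (section 10.1);
- assumed: bias b of 0.2 to 0.4 SD towards BFR in substituted values, share s substituted at a visit, and pre-post correlation ρ of 0.6 to 0.7.

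The standard error of the adjusted difference is √(1 − ρ²) × √(2/n). With n = 10 this is 0.800 × 0.447 = 0.358 SD at ρ = 0.6 and 0.714 × 0.447 = 0.319 SD at ρ = 0.7. The mean bias is s × b. Type I error comes from the noncentral t distribution with 17 df and noncentrality (s × b)/SE.

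| Share s | b (SD) | Mean bias (SD) | Bias/SE, ρ = 0.6 / 0.7 | Type I error, ρ = 0.6 / 0.7 |
|---|---|---|---|---|
| 0 | any | 0 | 0 | 5.0% |
| 25% (5 of 20) | 0.2 | 0.05 | 0.14 / 0.16 | 5.2% / 5.3% |
| 25% | 0.4 | 0.10 | 0.28 / 0.31 | 5.8% / 6.0% |
| 50% (10 of 20) | 0.2 | 0.10 | 0.28 / 0.31 | 5.8% / 6.0% |
| 50% | 0.4 | 0.20 | 0.56 / 0.63 | 8.3% / 9.1% |

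Simulating the planned ANCOVA with random substitution (40,000 runs per cell) gives 4.8% to 5.1% with none, 5.1% to 5.9% at 25% and 5.8% to 8.4% at 50%. These run slightly lower because the simulation fits the ANCOVA, including the slope on the pretest value, whereas the formula treats that slope as known.

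**Precision if therapy values are dropped.** The 95% half-width is the t quantile × SE:

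| Values kept | Per arm | df | SE (SD), ρ = 0.6 / 0.7 | Half-width (SD), ρ = 0.6 / 0.7 |
|---|---|---|---|---|
| 20 | 10 | 17 | 0.358 / 0.319 | 0.75 / 0.67 |
| 15 | 7.5 | 12 | 0.413 / 0.369 | 0.90 / 0.80 |
| 10 | 5 | 7 | 0.506 / 0.452 | 1.20 / 1.07 |

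**Cost of a repeat test.** Three 5-second attempts with two 2-minute rests take 15 + 240 = 255 seconds per leg. Both legs take 510 seconds, or 8.5 minutes, plus practice.

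**The case against.** The strongest reply is that the rule may never operate. It needs the same measurement, within about a week, with the result handed over. No section lists a dynamometer test as part of therapy, and MVC is absent from the items taken from therapy notes in sections 9.7 and 10.4. That stands, and it is why the size is conditional.

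Second, torque is read by a machine, and subjects know their arm in every test, including those run by the blinded tester. That also stands. Deleting the rule removes only the tester's contribution, and only for substituted values.

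Third, visits are approximate and have no stated windows, and a week's staleness has no stated direction by arm. MVC is also the first exertional test in the fixed order. The timing and order points are therefore secondary: they are more likely to add noise than bias.

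Fourth, a therapy value documented in Epic might be traceable, and the case report form is not available to check. The accurate statement is that the protocol does not require the source to be recorded.

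Fifth, the 9.1% maximum comes from the formula. The planned ANCOVA peaks at about 8.4%, and only if half of all values are substituted with a 0.4 SD bias.

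Finally, disclosing the exception and recording the source would settle the contradiction in the text without retesting anyone. It would not make the substituted values blinded. None of these points removes the conflict between sections 9.2 and 6.0.

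**Conclusion.** The concern holds. As written, section 9.2 can put strength values into the group comparison that were probably obtained by someone who knew the arm, against the unqualified statement in section 6.0.

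The effect on inference cannot be derived from the documents. It is nil with no substitution. Under the assumptions above, the bias is 0.05 to 0.10 SD with 5 of 20 values substituted and 0.10 to 0.20 SD with 10 of 20, against a standard error of 0.32 to 0.36 SD. That is small unless substitution is common. Confidence is medium, because the frequency of substitution and the tester's identity are not stated. The point should be fixed because the outcome is central to the aim and the remedy is cheap.

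**What to change.** Delete the substitution rule from section 9.2. Every MVC in the group comparison is then taken by the blinded tester at the scheduled visit, and any therapy values are kept as supplementary data. MVC is already on the Study Calendar for Visits 2 to 5. The cost falls only on subjects recently tested in therapy: a repeat practice set and about 8.5 minutes of testing, with some added fatigue or soreness.

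If the rule is kept, state the exception in section 6.0, record the source, date and tester of every MVC, and pre-specify a sensitivity analysis restricted to blinded-tester values. This is the weaker option. The restricted analysis loses the precision shown above. It also selects on something that happens after randomization: section 8.0 says "Subjects will progress through the goals set by their therapist as their condition permits", so having a recent therapy test may depend on progress, which the intervention could affect.

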9.3 Y-Balance Test

This test is used to assess lower body strength and balance. Study staff will demonstrate the test positions. With study staff within reach of subject, subject will have a practice trial and then will have 3 scored attempts. The greatest distance for each leg will be recorded for each of three positions (anterior, Posterior lateral, and medial lateral attempt to reach the most distance in each of the 3 positions. The maximum distance reached is recorded in cm. Subjects will perform this test with each leg.

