11.0 Risks and Benefits	17
11.1	17
Physical, Functional, Range of Motion Testing	17
11.2 Blood Flow Restriction device	17
11.3 DEXA Scan	18 17
11.4 InBody Bioelectrical Impedance scan	18
11.5 Confidentiality	18
11.6 Data Safety Monitoring Plan	18
12.0 Ethical Considerations.....	18
13.0 References	19

Use of Blood Flow Restriction + Standard of Care Physical Therapy to Improve Functional Outcomes after
Anterior Cruciate Ligament Reconstruction
PI: [name].
Institution: UAMS
Sponsor: UAMS

List of Abbreviations

ACL	Anterior cruciate ligament
BFR	Blood Flow Restriction
CRF	Case Report Form
DEXA	Dual-energy X-ray Absorptiometry
EMR	Electronic medical record
FDA	Food and Drug Administration
IRB	Institutional Review Board
MVC	Maximal voluntary contraction (of the quad muscles)
NIH	National Institutes of Health
PBFR	Personalized Blood Flow Restriction
PT	Physical Therapist
RIOA	Reynolds Institute on Aging
ROM	Range of Motion (of the knee joint)
UAMS	University of Arkansas for Medical Sciences
UPIRTSO	Unexpected problem involving risks to subjects or others

Study Schema

Surgeon collaborators or their designees screen their orthopedic clinic for eligible subjects and send referrals to study staff via UAMS email.

Study staff contact referrals via phone or email to discuss consent process.

Visit 1: Subjects come to RIOA for informed consent process prior to surgery.
Randomization (1:1) occurs.

Visit 2: Approx. 7-10 days prior to surgery, subjects come to RIOA for baseline testing.

Subjects undergo scheduled knee surgery at UAMS

***Prescribed physical therapy begins with or without BFR per randomization at UAMS
Colonel Glenn facility***

Visit 3: Subjects come to RIOA for post-operative testing approx. 8 weeks postop.

Prescribed physical therapy continues with/without BFR per randomization

Visit 4: Approx. 12 weeks postop, subjects come to RIOA for mid-point testing.

Visit 5: Approx. 16 weeks postop, subjects come to RIOA for end-point testing.

Use of Blood Flow Restriction + Standard of Care Physical Therapy to Improve Functional Outcomes after
Anterior Cruciate Ligament Reconstruction
PI: [name].
Institution: UAMS
Sponsor: UAMS

Study Calendar

Procedure	Visit 1	Visit 2	Visit 3	Visit 4	Visit 5
Informed consent	X				
10-meter walk test		X	X	X	X
bilateral MVC		X	X	X	X
DEXA scan		X	X	X	X
In Body scan		X	X	X	X
Stair ascent			X	X	X
Stair descent				X	X
Y-balance test			X	X	X

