4.0 Study Population

Up to 25 subjects of any gender or ethnicity will be enrolled with a target of n=20 for study completion.

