4.1 Inclusion Criteria

1. Men and women, ages 18-34 years.
2. Scheduled to undergo elective ACL surgery at UAMS.
3. Capable of providing informed consent.
4. Willing to exercise with BFR.
5. COVID-19 negative or asymptomatic.

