9.6 InBody Bioelectrical Impedance Analysis

This test will measure total body and segmental water, to be combined with the DEXA measures for a more accurate body composition estimates. To obtain measurements, subjects are asked to stand barefoot on a calibrated scale to obtain subject weight. Once subject height, sex, and age are entered into the device, subjects are instructed to hold onto two handles and remain still while an imperceptible electrical current runs between electrodes in the handles and scale. Total assessment time is <2 minutes. Subjects will be asked to fast for 8 hours, avoid caffeine and alcohol for 12 hours, and avoid strenuous exercise for 24 hours prior to this procedure.

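### Y-balance is scored as unscaled reach in cm and has no pre-surgery value, so nothing in the plan removes body-size variation from this outcome (a loss of precision, not a bias)

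*Combined protocol and SAP*

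**What the plan says.** Section 9.3 gives three scored attempts per position and keeps the best: "The greatest distance for each leg will be recorded for each of three positions". It continues: "The maximum distance reached is recorded in cm. Subjects will perform this test with each leg". It gives no division by leg length or height, no composite and no between-leg index.

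The Study Calendar marks Y-balance at Visits 3, 4 and 5 and leaves Visit 2 blank. The Visit 2 text in section 5.0 agrees. After body composition and a warm-up it lists only "strength testing of each leg, and 10-meter walking speed test will commence".

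Section 10.1 plans an ANCOVA for each strength and functional outcome, with intervention group and that outcome's own pretest as the only terms. Mixed models are a fallback if ANCOVA assumptions fail. No body-size or sex term is named in either case.

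Eligibility (section 4.1) is "Men and women, ages 18-34 years". Section 4.0 says: "Up to 25 subjects of any gender or ethnicity will be enrolled with a target of n=20 for study completion". Section 7.0 randomises 1:1 from a random list with no stated stratification. Height is entered for DEXA (section 9.5). For InBody (section 9.6) sex is entered as well: "Once subject height, sex, and age are entered into the device". Leg length is not collected.

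**The concern.** Reach is a distance made with the leg. It therefore reflects how long the leg is as well as the strength and balance that section 9.3 says the test assesses. A tall participant with moderate control can out-reach a short one with good control.

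MVC torque also depends on body size, but it is measured at Visit 2, and adjusting for that pretest absorbs much of the size difference between people. Y-balance has no such value, and the plan puts nothing in its place.

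Two things are at stake. First, the arm comparison for this outcome is noisier than it needs to be in a study with very few participants. Second, section 10.1 says the pilot's purpose is to supply data for powering later studies, and an SD that includes between-person size differences would feed into that calculation.

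**Working it through.** The documents state no effect size, SD or power for Y-balance, so there is no figure of theirs to reproduce.

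**Inputs from the documents:** 20 completers at 1:1, so 10 per arm; two-sided alpha 0.05.

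**Assumption, not in the documents:** within-arm correlation r between the body-size measure and raw reach of 0.3, 0.5 or 0.7. Results are in units of the raw-reach SD.

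**Formulas**
- Share of variance due to size = r².
- Participant equivalent of removing it = 1/(1 − r²). For example, 1/(1 − 0.09) = 1.10 and 1/(1 − 0.49) = 1.96.
- Residual SD after adjustment = √(1 − r²) × raw SD.
- Detectable difference and power come from the noncentral t, with 18 degrees of freedom unadjusted and 17 with one covariate.
- SD of the chance arm difference in mean body size = √(2/10) = 0.447 body-size SD. Its effect on the reach difference has a 95% range of ±1.96 × r × 0.447.

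| | Unadjusted | r = 0.3 | r = 0.5 | r = 0.7 |
|---|---|---|---|---|
| Variance due to size | – | 9% | 25% | 49% |
| Participant equivalent | 1.00 | 1.10 | 1.33 | 1.96 |
| Residual SD (raw = 1) | 1.00 | 0.95 | 0.87 | 0.71 |
| Detectable difference, 80% power (SD) | 1.32 | 1.27 | 1.15 | 0.95 |
| Power for a 1-SD effect | 56% | 60% | 68% | 84% |
| Shift from chance size imbalance, 95% range, if unadjusted (SD) | – | ±0.26 | ±0.44 | ±0.61 |

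**How often imbalance arises.** An arm difference in mean body size above 0.5 SD has probability 2 × [1 − Φ(0.5/0.447)] = 26%. If half the participants are men, the arms differ by three or more men in 26% of allocations (22% if 30% or 70% are men).

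**Type I error.** In 200,000 simulated trials with no treatment effect, the unadjusted test rejected in 0.049 (r = 0.5) and 0.050 (r = 0.7), so it is valid overall. Among the 26% of trials with a size imbalance above 0.5 SD, it rejected in 0.094 and 0.134. In the remaining trials it must therefore reject less than 5% of the time: (0.0494 − 0.262 × 0.094)/0.738 ≈ 0.034 for r = 0.5, and (0.0502 − 0.263 × 0.134)/0.737 ≈ 0.020 for r = 0.7.

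**The case against.** **Bias.** A reader might infer that body size biases the arm comparison, or that a chance height difference would pass as a treatment effect. The documents do not support that. Allocation is randomised, and the unadjusted standard error already contains the size variance. At 10 per arm the 95% interval has a half-width of about 2.10 × 0.447 = 0.94 SD, and the typical imbalance shifts of 0.26 to 0.61 SD lie inside it. This objection stands, and the point is confined to precision and exposure to imbalance.

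**Size.** The magnitude rests on an assumed r. At r = 0.3 the gain is slight: 1.32 to 1.27 SD detectable. A higher floor can be reached by treating reach as exactly proportional to leg length, but nothing in the documents establishes that. If leg length is the driver, height is only a proxy, and its r may sit lower in the range. This also stands.

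**Recorded is not analysed.** Section 9.3 describes data capture, whereas section 9.4 says which stair value enters the analysis. Strictly, the analysed Y-balance value is undefined. That is a fair reading, but an undefined value does not remove body size either.

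**Existing remedies.** Three can be suggested, and none works:
- Section 9.8 lists Y-balance in a test order for all visits. It sets sequence, and neither the Calendar nor the Visit 2 text schedules the test before surgery.
- Visit 3 could serve as the pretest. It falls after randomisation and after therapy with or without BFR has begun, so adjusting for it could remove part of the treatment effect.
- The mixed-model fallback is triggered only by failed assumptions and names no size term.

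**Wording of the third direction.** A reader might also fault how section 9.3 names it. That sentence is broken and may be tracked-change residue, so nothing here relies on it.

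**Weight.** This is a pilot with several outcomes and no designated primary, and height and sex can be used later. That limits the importance. It does not argue against prespecifying now.

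**Conclusion.** The point holds as a loss of precision. Y-balance is recorded as raw cm in a mixed-sex sample, the only covariate in section 10.1 is unavailable for it, and no alternative is named although height and sex are already collected. For r between 0.3 and 0.7, body size takes up 9% to 49% of the variance, equivalent to about 1.1 to 2.0 times the participants for this outcome. The factual gap is certain from the text. The size of the gain is not, because r is assumed.

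For planning, the raw SD would exceed the size-adjusted SD by a factor of 1/0.95 = 1.05 to 1/0.71 = 1.4. That matters if the later study adjusts for size; if it does not, the raw SD is the relevant one.

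Importance is moderate: worth correcting because it is nearly free, but no threat to the validity of the trial. Stair ascent and descent also lack a Visit 2 test, so the missing-pretest gap in section 10.1 reaches them too, but the figures here concern Y-balance only.

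**What to change.** In sections 9.3 and 10.1, before arms are compared:

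- State that Y-balance reach is analysed by ANCOVA with baseline height and sex as covariates in place of the pretest that does not exist. Reach divided by height is an acceptable alternative, though it assumes proportionality and the covariate model does not.
- Use one height per participant, taken from the Visit 2 scan entry, and state how it is measured.
- Allow scaling to leg length only as an option where it is measured. It is not collected now, and a Visit 2 measurement cannot be obtained for anyone already past that visit.
- Report raw cm descriptively, and give both the raw and the adjusted SD for future planning.
- Rule out the Visit 3 value as the pretest. Do not scale to the non-surgical leg: the Background (section 2.0) cites a study reporting contralateral strengthening with BFR, so that leg may itself respond to treatment.

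The cost is a sentence or two of text and one or two of the 18 residual degrees of freedom. The height-based options need no new measurement and can be applied to data already collected.
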